7.2.2. Secondary efficacy endpoints

Difference between the treatment arms in the proportion of completely sober patients during a 4-week period at 6 and 12 months, respectively.

The proportion of completely sober patients is measured with TLFB. To be considered sober, the patient must have entered 0 standard glasses consumed during the 4-week period preceding the 6- and 12-month visits, respectively.

The difference in the total amount of alcohol consumed per 4-week period after 6 and 12 months, respectively, compared with baseline

The total amount of alcohol consumed per 4-week period is measured in standard glasses using TLFB, and is the sum of the number of glasses for the entire period. How to determine the TLFB at baseline is stated in section 8.1.2. Follow-up TLFB is then made at each visit. The difference in the number of heavy drinking days per 4-week period at 6 and 12 months, respectively, compared with baseline

The number of heavy drinking days is measured with TLFB. Heavy drinking days are the same as days with heavy consumption, which means consumption of 4 or more standard glasses of alcohol per day for women and 5 or more standard glasses of alcohol per day for men. How to determine the TLFB at baseline is stated in section 8.1.2. Follow-up TLFB is then made at each visit.

The difference in the number of drink-free days per 4-week period at 6 and 12 months, respectively, compared with baseline.

The measuring tool becomes TLFB where the number of days of consumption specified as zero standard glass during a four-week period can be calculated. How to determine the TLFB at baseline is stated in section 8.1.2. Follow-up TLFB is then made at each visit..

The measuring tool becomes TLFB where the number of days of consumption specified as zero standard glass during a four-week period can be calculated. How to determine the TLFB at baseline is stated in section 8.1.2. Follow-up TLFB is then made at each visit.

The measuring tool becomes TLFB, where the sum of the number of standard glasses for the entire 4-week period is divided by the number of days when alcohol is consumed. How TLFB is to be determined at baseline is stated in section 8.1.2. Follow-up TLFB is then made at each visit.

Time to relapse

Depending on the goal of treatment, a relapse can be either a day of heavy consumption or drinking at least one standard glass of alcohol. Both recurrence measures will be evaluated.

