- The number of days before the first alcohol intake (at least one standard glass) according to the patient's own information.
- The number of days before the first heavy drinking day according to the patient's own information.

Clinical Global Impression improvements after 6 and 12 months, respectively

The patients who after 12 months are "significantly improved" or "greatly improved", ie they receive a value of 1 or 2 on the CGI-I scale (see section 8.3.6) are considered to have responded to the treatment (responders). Patients with a value of 3 or higher are classified as non-responders. The proportion of responders will be compared between the treatment arms.

Change in quality of life measured with EQ-5D

EQ-5D is an accepted and widely used measure of quality of life, and the form is recommended by TLV (Dental and Pharmaceutical Benefits Agency). A general quality of life measure such as EQ-5D provides an overall picture of the study participants' perceived health, and is a good basis for health economic analyzes.

AUDIT improvement

The National Board of Health and Welfare prioritises AUDIT as a tool for identifying alcohol problems. The treatment arms will be compared with respect to:

- Proportion of patients who after 12 months have lowered their AUDIT score
- Proportion of patients who after 12 months have lowered their AUDIT score to at least one zone
- Proportion of patients who after 12 months have a risk level <II
(i.e. less than 6 AUDIT points for women, 8 AUDIT points for men).

SADD improvement

Change in alcohol dependence measured as the difference in SADD scores at 12 and 6 months, respectively, compared with baseline).

Compliance with agreed treatment

The patient remains in treatment

At each study-related visit, it is documented whether the patient remains in treatment or has interrupted his or her treatment. The proportion of patients who remain in treatment will be compared between the patient groups over time.

Compliance with TripleA

For the TripleA arm, the proportion of measurements performed compared to announced measurements will be reported. The information is retrieved from the TripleA database where all notifications and measurements are logged. Corresponding information is not available for the control arm for obvious reasons.

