7.3.2. Alcohol calendar– Time-Line Follow-Back

Time-Line Follow-Back (TLFB) is a method that can be used to obtain information about patients' alcohol consumption. (Sobell, Maisto et al 1979). In short, it means that as far back as 3 months ago, you retrospectively reconstruct how many standard glasses you have consumed per day. It is accepted that the reporting is not an exact representation of the alcohol intake, but also that it

provides a decent benchmark, which is also sensitive to changes in the drinking pattern. An alcohol calendar (see Appendix C) is used for this purpose. For study purposes, alcohol consumption reported via TLFB is used for the 4 weeks preceding each visit. How to determine the TLFB at baseline is stated in section 8.1.2.

When filling in TLFB, the patient and therapist must consult and results of blood tests and for the intervention arm, TripleA measurements must also be taken into account to identify if and when alcohol intake has occurred.

Information about missed measurements or measurements that show alcohol in the exhaled air (both for TripleA and for regular measurements at the care provider) should be used in the TLFB call and should in the alcohol calendar correspond to a number greater than 0 standard glasses on the current day. There may be discrepancies between what the patient is willing to state in the TLFB and the information that the caregiver has available in the TripleA caregiver portal or from other sources. The caregiver should talk to the patient about this, and give the patient the opportunity to update the information in the TLFB if necessary, but should not force the patient to enter a number greater than 0 or change information provided by the patient without the patient's consent.

In CRF, it is possible for the care provider to state whether there are signs of alcohol intake that do not correspond to reported intake in TLFB.

Time: At each visit.

AUDIT (The Alcohol Use Disorders Identification Test)

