7.3.12. TripleA

Random measurements of alcohol in exhaled air, with identity control via mobile camera. Made on request via notification in mobile app - only in the TripleA arm. Reporting of results to the therapist takes place via the caregiver portal.

Timing: Sleep breaks can be added by a therapist. Thereafter, the alcohol tests take place according to schedule daily just before and after the sleep break. A third alcohol test will take place during the waking time between the 2 previous tests. If desired, this can be planned to happen randomly.

The care provider checks the care portal before each patient visit, but does not have continuous supervision of the system within the framework of the study, which is technically but not organizationally possible.

In order for TripleA to always be usable, the mobile phone has been provided with a subscription that allows free calls and SMS, as well as data traffic up to 1GB per month. Kontigo Care is responsible for the subscription fee. The patient can use the phone during the study at no extra cost.

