7.7. Subjects

7.7.1.Inclusion criteria for selection of subjects

- Patients for whom there is a care commitment for the alcohol program at the Addiction and Neuropsychiatry, Akademiska sjukhuset
- 18 years or older
- Meets at least 2 of the criteria for addiction / substance syndrome according to DSM-5
- Ability to understand and communicate in Swedish
- Ability to handle the technical equipment used in the study (breathalyzer + smartphone)
- Has a fixed point (accommodation, night rest place to charge the phone)

7.7.2.Exclusion criteria for selection of subjects

- Schizophrenia
- Substance syndrome related to substances other than alcohol and nicotine
- Impaired lung function (not able to achieve adequate exhalation volume for breathalyzer function)
- The patient is cared for within the framework of LVM
- Unsuitable to participate in the study according to the examiner's assessment
- Has not consumed any alcohol during the 4 weeks that baseline Time Line Follow Back refers to.
- Normalized CDT and PEth values in blood samples taken at visit 1.

7.7.3.Criteria and procedures for removing subjects from the study or suspending their participation

Substance syndrome related to substances other than alcohol and nicotine: Screening with urine sample and DUDIT is done at inclusion. The test result does not have to be available before the subject is included in the study, but should a positive screening test be reported, the subject should be removed from the study. No further samples are taken within the framework of the study.

Should the patient lose or otherwise lose the test product, it can be replaced (a limited number of times) and the patient does not need to be removed from the study if alcohol consumption is reported during the days when the measurements could not be performed and blood tests are performed to determine a new level of PEth / CDT . Phones that have fallen into the wrong hands or are misused in other ways can be deactivated by Kontigo Care. Contact Kontigo Care should this occur.

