The efficacy measures based on self-reported TLFB data may be affected if patients provide incorrect information in an attempt to protect their addiction and to conceal their possible drinking. In this study, the probability of a recurrence being detected is lower in the control arm than in the TripleA arm. This risks giving an incorrect comparison as frequent measurements in the TripleA arm (at least 3 times a day) increase the possibility of detecting the use of alcohol, which would otherwise have gone unnoticed. TLFB data can also be affected and provide more honest reporting as the patient knows that even shorter relapses risk being detected through the frequent alcohol tests. This could mean that even if the actual alcohol use in the TripleA arm is lower than in the control arm, we get more reports of alcohol use in the TripleA arm.

However, it is reasonable to assume that even if more alcohol intake is detected with TripleA, the actual alcohol intake pattern is not worse in the TripleA arm than in the control arm. It is also an advantage that relapses and alcohol intake become clear to both the patient and the therapist, in order to be able to work with relapses and the factors that trigger them within the framework of the treatment. The earlier you can stop a risky alcohol intake, the less the consequences for both the patient and the environment.

Although more relapses would be detected in the TripleA arm due to the frequent measurements, there is a possibility that the support that the system provides to maintain sobriety leads to more patients completing the entire treatment and participating in aftercare throughout the study period. Our hypothesis is therefore that the proportion of patients without heavy drinking days is more and the proportion who carry out the entire aftercare is more in the arm where the care and aftercare has been strengthened with TripleA.

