9.1.2.2. Secondary efficacy endpoints

- i) Change in total amount of alcohol consumed per 4-week period after 6 months from "baseline." An ANOVA model for repeated measurements will be used to compare the groups.
- ii) Change in total amount of alcohol consumed per 4-week period after 12 months from "baseline." An ANOVA model for repeated measurements will be used to compare the groups.
- iii) Proportion of completely sober patients at 12 months A logistic regression model will be used to compare the groups.
- iv) Proportion of completely sober patients at 6 months. A logistic regression model will be used to compare the groups.
- v) Change from baseline in the number of heavy drink days per 4-week period at 6 and 12 months, respectively. An ANOVA model for repeated measurements will be used to compare the groups.
- vi) Change from "baseline" in the number of non-drinking days per 4-week period at 6 and 12 months, respectively. An ANOVA model for repeated measurements will be used to compare the groups. Förändring från "baseline" i antalet standardglas per dryckesdag per 4-veckorsperiod vid 6 och 12 månader, respektive. vii) Time to relapse (ie first alcohol intake). For

patients with the goal of becoming alcohol-free, relapse is defined as the first day after "baseline" where alcohol consumption was found, while relapse for patients with the goal of reducing alcohol consumption is defined as the first day after "baseline" where heavy alcohol consumption is found. Heavy consumption is defined for women as a day with 4 or more glasses, while for men it is defined as a day with 5 or more glasses. The data sources TripleA, TLFB or blood samples are used to detect recurrence. To compare the survival curves, ie. the variable time to recurrence, between the treatment groups a log-rank test will be used.

- vii) CGI improvement. The proportion of respondents at follow-up visits is compared between the groups with a logistic regression model.
- viii) EQ-5D. The groups are compared regarding change from "baseline" with ANOVA model. No significant difference is expected, as quality of life forms are generally not particularly sensitive to change after treatment.
- ix) Participation in treatment. To compare the survival curves, ie. the variable time until the treatment is stopped, between the treatment groups a log-rank test will be used.

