9.2. Sample size, significance level and statistical strength

The primary endpoint is the proportion of patients who do not have heavy drinking days during a 4-week period after 12 months from baseline. Assuming that the proportion is 30% in the control group and you want to be able to detect a difference of 30% between the TripleA and the control group, 42 patients are needed per treatment group to achieve a strength of 80% with a double-sided test of 5% significance level. Assuming that the proportion of patients who do not complete the study is about 20%, a total of 106 patients need to be randomized, ie 53 per group.

Expected loss

The drop-out rate in alcohol studies is usually quite large.

At inclusion, the patient is asked to provide at least one contact person that the study staff can contact if the patient is absent from agreed meetings, interrupts treatment and / or stops blowing. Patients who do not wish to continue their treatment should be informed that they are welcome to continue using TripleA and / or alcohol, or otherwise report their alcohol consumption, as this is valuable information for the study. If the patient wants to stop the study completely, the study staff should at least ask the question "how many standard glasses have you drunk the most in one day since we were last seen?". This gives the opportunity to assess whether there has been a heavy drinking day or not.

A certain loss of patients during the course of the study is expected. Three types of missing data can be identified.

1. Patients who choose to discontinue treatment and study participation.
2. Patients who choose to discontinue treatment but who continue to provide information on alcohol intake (i.e. remain in the study)

Patients who continue treatment but who do not provide complete information on alcohol intake.

4. Patients who miss occasional visits.

All efficacy evaluations will be performed on two analysis populations, a population consisting of all randomized patients contributing efficacy data from at least one baseline visit (ITT) and a population consisting of all patients who completed the study according to the protocol (PP).

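### The between-arm log-rank test of time to relapse counts TripleA detections, which exist in one arm only, so it mixes relapse with detection, mainly against TripleA

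*Combined protocol and SAP*

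**What the plan says.** Three sections describe this endpoint, and they differ.

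- **Section 9.1.2.2, item vii.** "The data sources TripleA, TLFB or blood samples are used to detect recurrence". Relapse is the first day with any alcohol for patients aiming at abstinence and the first heavy drinking day for patients aiming at reduction. Time runs from baseline and the arms are compared by log-rank.
- **Section 7.2.2.** The source is self-report: "The number of days before the first alcohol intake (at least one standard glass) according to the patient's own information", with a matching item for the first heavy drinking day. It adds: "Both recurrence measures will be evaluated".
- **Section 9.1.3 (exploratory).** TLFB-based primary and secondary analyses will be compared with versions that also use blood and TripleA results.

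On the data sources:

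- **TripleA (Section 7.3.12):** "Made on request via notification in mobile app - only in the TripleA arm". Section 7.8.11 gives at least three tests a day.
- **TLFB (Section 7.3.2):** "For study purposes, alcohol consumption reported via TLFB is used for the 4 weeks preceding each visit". The follow-up visits in Section 7.3.14 are at months 1, 2, 3, 6 and 12.
- **Blood:** PEth and CDT are tied to the same visits and reflect recent weeks (Section 7.3.7).

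Section 7.8.11 acknowledges: "In this study, the probability of a recurrence being detected is lower in the control arm than in the TripleA arm".

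**The concern.** A log-rank test compares relapse only if relapse is looked for equally in both arms. Here a relapse in the TripleA arm can be dated to the day at any time in the year. A control relapse outside a TLFB window is dated late, or missed if drinking stops before the next window. With no true difference, the TripleA arm tends to appear to relapse earlier, and a true delay is harder to show.

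Whether relapse can be delayed is a stated secondary objective (Section 6.1.2), and this endpoint answers it. Separately, two analysts following the plan could define the event, its source and its time zero differently.

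The event rule also has a gap. For reduction-goal patients the event is a heavy drinking day, but Section 9.1.2.2 only illustrates how breath results might correspond to one. It does not say which TripleA results count.

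**Working it through.** **1. The plan's own figure.** Section 9.2 sizes the primary endpoint only: 30% against 60%, two-sided 5%, 80% power. Pooled formula: [1.96·√(2·0.45·0.55) + 0.842·√(0.30·0.70 + 0.60·0.40)]² / 0.30² = 41.97, so 42 per arm. Then 42/0.8 = 52.5, so 53 per arm and 106 in total. This reproduces and is not in dispute. No event count or power is given for time to relapse.

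**2. Days covered by TLFB.** With visits at days 30, 61, 91, 182 and 365, the windows are days 3-30, 34-61, 64-91, 155-182 and 338-365.
- Coverage: 5 × 28 = 140 days; 140/365 = 38%.
- First 91 days: 3 × 28 = 84 covered.
- Long gaps: days 92-154 (63 days) and 183-337 (155 days).

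Blood does not date relapses in the long gaps, because it reflects recent weeks.

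**3. Assumed drinking patterns.** The documents give no relapse-time distribution. The assumption is an exponential time to first relapse, then drinking on a share p of later days. Section 9.2 limits the choice: "Assuming that the proportion is 30% in the control group" with no heavy day in the last four weeks, so at least 70% drink in that window. The share drinking then is F(337)·[1 − (1 − p)^28] + [F(365) − F(337)].
- Median 180 days, p = 0.10: 0.727 × 0.948 + 0.028 = 0.717. Compatible.
- Median 360 days, p = 0.30: 0.477 × 1.000 + 0.027 = 0.505. Not compatible.

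Medians of 14-180 days with p of 0.10-0.30 are compatible. Drinking on 3% of days gives at most 0.574 and is not.

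**4. No true difference.** Simulated two-sided rejection at nominal 5%, 53 per arm, 4,000 runs, p = 0.10 / 0.30. Every detected drinking day counts as an event, and TripleA detects all drinking days.

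| Median relapse | As written | Of which against TripleA | Half with a reduction goal, no TripleA event counted for them |
|---|---|---|---|
| 14 days | 0.072 / 0.059 | 0.060 / 0.042 | 0.054 / 0.054 |
| 30 days | 0.098 / 0.072 | 0.090 / 0.065 | 0.064 / 0.063 |
| 90 days | 0.200 / 0.150 | 0.199 / 0.147 | 0.088 / 0.077 |
| 180 days | 0.112 / 0.100 | 0.108 / 0.094 | 0.066 / 0.061 |

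If TripleA detects only half of drinking days, the as-written column becomes 0.051-0.077 (14-30 days) and 0.093-0.173 (90-180 days). With 20% drop-out it is 0.056-0.173. Visit-grouped analysis on common sources gives 0.045-0.056.

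**5. True hazard ratio 0.6.** Power is 31-40% as written against 54-67% for visit-grouped analysis on common sources (90-180 days), and 41-67% against 66-70% (14-30 days).

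**6. A different relapse model.** Gamma-mixed daily rates, mean 3, 10 or 30 relapse days a year, 42 per arm. The calendar gap alone gives significance against TripleA in 12-43% of null trials. These settings were not limited by Section 9.2. With shape k, the share clean over 28 days is (1 + 28μ/(365k))^(−k): 0.81 (μ = 3, k = 1), 0.60 (μ = 10, k = 0.7) and 0.36 (μ = 30, k = 0.7), all above 0.30. The closest setting, 30 days a year, gives the 12%. Under this model, power with equal detection is only 18-24% for a 40% lower relapse-day rate, so the power gain in step 5 depends on the model.

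**7. Which common sources?** Suppose 10% of controls hide all drinking in TLFB, and blood detects 30% or 60% of windows with drinking (both assumed). Null rejection:

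| Median | As written, blood included | TLFB only, by visit | TLFB plus blood, by visit |
|---|---|---|---|
| 14-30 days | 27-37% or 15-25% | 37-50% | 12-20% or 6-8% |
| 90-180 days | 10-40% | 12-22% | 6-9% or 5-6% |

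**8. PEth carry-over.** With the 4-7 day half-life in Section 4.6, the share of the visit 1 level left at day 30 is 2^(−30/4) = 0.006 to 2^(−30/7) = 0.051.

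**The case against.** The strongest reply is that the plan knows of the problem and it may be small. Section 7.8.11 discloses it. The bias runs mainly against the sponsor's own product. The endpoint is secondary. Relapse may also come early, inside the nearly continuous first three months, since patients are excluded for "Normalized CDT and PEth values in blood samples taken at visit 1". All of this limits the severity. None of it tells an analyst which test to run, and the plan gives no relapse-time distribution on which to rely.

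Five stronger readings are tempting, and the documents do not support them.

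- **Section 9 offers nothing against the bias.** Section 9.1.3 foresees a TLFB-based version. The gap is that it sits under exploratory work and does not say which version is the main one.
- **Section 7.2.2 requires both relapse measures in every patient.** It says both will be evaluated, but it too introduces relapse as depending on the treatment goal. The conflict over data source is firm; this one is partial.
- **The clock is defined to start before enrolment.** Sections 7.1.2 and 7.8.2 describe a pre-enrolment window for baseline data, while Section 9.2 counts 12 months from baseline, which fits month 0. This is an ambiguity.
- **TLFB alone would cure the problem.** With some concealment it can do worse than the current rule when relapse is early (step 7). Section 7.1.3.2 names biomarkers as the reliability check on TLFB.
- **A clean window shows no relapse since the last visit.** At months 6 and 12 it does not, because 63 and 155 days before those windows are unobserved.

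**Conclusion.** The point holds. The test as written lets a source that exists in one arm supply events for a comparison between arms, and its definition conflicts with Section 7.2.2. The contradiction is firm. The direction, mainly against TripleA, is firm as long as device detection is at least as good as control detection; it could weaken where breath results fail to identify heavy days.

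The size is not firm. Under patterns compatible with Section 9.2, null rejection is about 9-20% for median relapse at 90-180 days. It is about 5-10% if relapse is early, or if half the patients have a reduction goal and no TripleA result counts for them. These figures assume exponential relapse times and complete TLFB reporting within the windows.

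The primary endpoint and its sample size are unaffected by this rule. It should be fixed because it decides a stated secondary objective and the change is cheap.

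**What to change.** Reconcile Sections 7.2.2, 9.1.2.2 and 9.1.3, and name one main version. For the main between-arm test:

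1. Start the clock at randomisation (visit 1).
2. Use only sources collected on the same schedule in both arms: TLFB plus scheduled PEth and CDT samples, under one identical pre-stated rule. TripleA results do not count as events. Leave out the extra samples that Section 7.5.2 allows for missing breath values. State how PEth carried over from visit 1 is handled at month 1. Give TLFB alone as a sensitivity analysis.
3. Group by visit. Name the endpoint as the first assessment window (months 1, 2, 3, 6, 12) with relapse. Do not treat a clean month 6 or 12 window as proof of no relapse in the unobserved days before it.
4. Report both relapse measures of Section 7.2.2.

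Report day-level TripleA-detected relapse descriptively in the TripleA arm, with a stated rule for which results count. Keep the version that adds TripleA data as the exploratory comparison of Section 9.1.3.

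State as a limitation that device results inform TLFB in the TripleA arm (Sections 7.3.2 and 7.8.3.2), so the asymmetry is reduced and not removed.

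The cost is SAP wording and slightly different survival code, with no new data. Day-level resolution is lost in the between-arm test.
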